- To compare the disability, quality of life and survival rate at ICU discharge, 3 and 6 months of patients who were admitted to ICU due to severe COVID-19 or other causes during high and low bed occupancy in the pandemic;
- To describe the sedentary behaviour and physical activity levels in a sample of ICU survivors during the COVID-19 pandemic using a one-week actigraphy protocol;
- To explore the psychological and emotional experiences reported by family members/next of kin of patients admitted to the ICU during the COVID-19 pandemic;
- To explore the emotional, intellectual, physical and administrative challenges faced by the participating ICU staff during the COVID-19 pandemic;
- To evaluate the feasibility of the follow-up from ICU discharge to 3 and 6 months during the pandemic.

METHODS

Study design and setting

The “Impact on Mental, Physical, And, Cognitive functioning of Critical care Time due to COVID-19” (IMPACCT-COVID19) is a prospective, multicentre, cohort study in seven Chilean academic medical-surgical ICUs. This study also involves a

qualitative component including semi-structured interviews with family members/next of kin of ICU survivors and with ICU staff from the participating centres. Participating sites are four public and three private hospitals comprising a pooled bed capacity of about 200 ICU beds for both COVID-19 patients and patients admitted for other causes. The IMPACCT-COVID19 study started in October 2020. Data collection is planned until November 2021 to achieve completion of the study in February 2022.

Study population and eligibility criteria

Adult patients (≥ 18 years old) who are mechanically ventilated for at least 48 hours in one of the participating ICUs and do not meet any of the exclusion criteria (**Table 1**) will be invited to participate.

Table 1. Exclusion and stopping follow-up criteria

Exclusion criteria	Rationale
Unable to walk independently 2 weeks prior to ICU admission (with or without a gait aid)	Potential confounding factor
S5q < 5 or CAM-ICU positive within 72 hours after ICU discharge	Unable to evaluate
Patient who do not understand or speak Spanish	Unable to evaluate
Patient unable to communicate verbally	Incomplete assessment data
Burn or severe trauma as admission diagnosis	Incomplete assessment data
Any neurological disorder (i.e. spinal cord injury, stroke and brain tumours) as admission diagnosis	Potential confounding factor

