The HADS is an interviewer or self-administered questionnaire designed to identify anxiety and depressive symptoms in a wide variety of in-hospital patients, which requires between 2 and 5 minutes to be completed.[28] The HADS has fourteen questions, seven for anxiety and seven for depressive symptoms. Each question is rated with a 4-point scale ranging from 0 ("absence") to 3 ("extreme presence"), resulting in a sum score of 21 points per subscale. HADS will be evaluated at ICU discharge and by telephone at 3 and 6 months using the Chilean version.[29]

Impact of Events Scale–Revised (IES-R)

The IES-R is an interviewer or self-administered questionnaire designed to measure the subjective distress caused by traumatic events that has been validated for critical illness survivors.[30] It comprises 22 questions divided in three subscales: intrusion, avoidance, and hyperarousal. Questions are rated in a 5-point scale ranging from 0 ("not at all") to 4 ("extremely"). The estimated response time is 6 minutes. It will be evaluated at ICU discharge and by telephone at 3 and 6 months using the available Chilean version.[31]

European Quality of Life Health Questionnaire (EQ-5D-3L)

The EQ-5D-3L is an interviewer or self-administered questionnaire of health status or health-related quality of life, including five domains: mobility, self-care, usual activities, pain/discomfort, anxiety/depression and global health state.[32,33] Each domain is scored based on 3 levels of severity: no problems, some problems, and extreme problems. Additionally, EQ-5D-3L includes a Visual Analog Scale ranging from “best imaginable health state” (100) to “worst imaginable health state” (0). Both parts of the questionnaire take an estimated response time of 2 minutes. It will be evaluated by telephone at 3 and 6 months using the Chilean version.[34]

Employment status

The employment status will be evaluated at ICU discharge, 3 and 6 months using tailored questions regarding current occupation, working hours, and any changes to their employment situation as it has been used elsewhere.[35,36]

Survival

The survival rate will be measured by the percentage of patients still alive at ICU discharge, 3 months, and 6 months after ICU discharge. Information on deaths will be obtained from death certificates from the Chilean National Civil Registry.

Sedentary Behaviour and Physical Activity

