The trajectory for each outcome measure will be estimated using longitudinal multilevel regression with robust standard errors to account for data coming from

seven treatment centres. If data have a normal distribution, a linear regression model will be chosen. In the case of right skewed data, a Poisson regression will be used. For HADS, IES-R and WHODAS 2.0, data will be analysed as total scores and categories given by each questionnaire.

Survival will be analysed using Kaplan-Meier curves. If the assumption of proportional hazards is met, survival will be compared between patients admitted due to COVID-19 vs. other causes using Cox regression. All analyses will be performed in Stata 16.0 SE.

Qualitative analysis

Data from the interviews with family members and critical care staff will be analysed using framework analysis.[43] Transcription will be aided by the software Scrintal and analysis by Nvivo 12.0. Two coders will listen and read in-full all interviews before meeting to explore potential common topics that were discussed during the interviews. These topics will form the initial coding framework. Through an iterative process these codes will be refined into overarching themes capturing differences and similarities across subgroups. A more advanced coding framework will be reviewed with members of the research team until agreement regarding the final framework is reached.

Themes will be used to explain the experience of family members during the pandemic and, potentially, identify areas where improvements could be made in the future. In the case of critical care staff, the aim is to explore to what extent the approach to the pandemic of each centre influenced the experience of the different clinical groups, and what can be learned for future outbreaks.

Findings will be shared with our participants and with other family members/ critical care staff that did not participate in the interviews to ensure our interpretation reflects their experiences.

Patient and public involvement

Patients or the public were not involved in the design, conduct, reporting, or dissemination plans of this study.

ETHICS AND DISSEMINATION

Ethical considerations

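### The Cox comparison of survival by COVID-19 status names no centre term, so its hazard ratio can be confounded by hospital, in an unknown direction

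*Combined protocol and SAP*

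**What the plan says.** All statements are in the combined protocol and SAP.

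- **Quantitative analysis, trajectories.** Outcome trajectories are estimated by "longitudinal multilevel regression with robust standard errors to account for data coming from" the seven centres. A linear or a Poisson form is chosen according to the distribution.
- **Quantitative analysis, survival.** This has its own paragraph. "Survival will be analysed using Kaplan-Meier curves", and then, if proportional hazards holds, "survival will be compared between patients admitted due to COVID-19 vs. other causes using Cox regression". Nothing in the paragraph says how centre is handled.
- **Study design and setting.** "Participating sites are four public and three private hospitals", with beds for both patient groups.
- **Secondary objectives.** The first begins "To compare the disability, quality of life and survival rate at ICU discharge, 3 and 6 months of patients", so the survival contrast is a stated aim.
- **Survival (outcome section).** "Information on deaths will be obtained from death certificates from the Chilean National Civil Registry".

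No other section adds a centre term to the survival analysis. Elsewhere in Quantitative analysis, treatment centre appears only as a subgroup for descriptive frequencies.

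**The concern.** COVID-19 status is observed, not allocated, so nothing in the design balances it across hospitals. Public and private hospitals may differ in the share of COVID-19 patients they discharge from ICU, and also in mortality after discharge for reasons unrelated to the diagnosis. If both differ, a Cox model with COVID-19 as its only term mixes the within-hospital contrast with the difference between hospitals. Its interval also ignores any clustering by centre.

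The plan itself gives reasons to expect hospitals to differ. The Introduction says that rapid bed expansion may have affected quality of care, and the qualitative work sets out to learn how each centre's approach shaped staff experience. Centre is recognised in the trajectory models and then absent from the survival comparison. At stake is whether the survival result in the first secondary objective can be read as a contrast by diagnosis.

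**Working it through.** The plan states no number of deaths, hazard ratio or power for survival, so there is no figure of its own to reproduce. The check asks how far a pooled hazard ratio can move from 1 when COVID-19 has no effect.

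**Inputs from the plan.** Seven centres, four public and three private (Study design and setting); 550 patients recruited (Sample size calculation). The abstract gives 450, but the closed-form ratio does not depend on the total.

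**Assumptions.** Centres of equal size, a constant hazard over 6 months, COVID-19 shares (c) of 40% to 80%, and 6-month mortality (m) of 4% to 12%. The documents give neither shares nor mortality by hospital.

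**Formula.** With weights w of 4 (public) and 3 (private), and h = −ln(1 − m):

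- rate with COVID-19 = Σ(w·c·h) / Σ(w·c)
- rate without = Σ(w·(1 − c)·h) / Σ(w·(1 − c))
- pooled ratio = the first divided by the second

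**Upper end: share 80% public, 40% private; mortality 12% and 4%.**

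- h = 0.1278 and 0.0408
- with COVID-19: (4×0.80×0.1278 + 3×0.40×0.0408) / (3.2 + 1.2) = 0.1041
- without: (4×0.20×0.1278 + 3×0.60×0.0408) / (0.8 + 1.8) = 0.0676
- ratio = 0.1041 / 0.0676 = 1.54

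**Lower end: shares reversed (40% public, 80% private), same mortality.**

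- with COVID-19: (4×0.40×0.1278 + 3×0.80×0.0408) / (1.6 + 2.4) = 0.0756
- without: (4×0.60×0.1278 + 3×0.20×0.0408) / (2.4 + 0.6) = 0.1104
- ratio = 0.0756 / 0.1104 = 0.68

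The same formula gives:

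| COVID-19 share, public / private | 6-month mortality, public / private | Pooled ratio, no true effect |
|---|---|---|
| 80% / 40% | 12% / 4% | 1.54 |
| 70% / 50% | 8% / 6% | 1.06 |
| 60% / 60% | 10% / 5% | 1.00 |
| 80% / 40% | 10% / 10% | 1.00 |
| 45% / 75% | 10% / 5% | 0.82 |
| 40% / 80% | 12% / 4% | 0.68 |

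Bias therefore needs both factors to vary, and it can go either way.

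**Simulation (550 patients, seven centres, true hazard ratio 1, 300 to 400 cohorts per scenario).**

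- *Share 75% / 45%, mortality 10% / 5%, about 43 deaths.* The pooled hazard ratio was 1.25 and the centre-stratified one 1.00. Repeat runs gave 1.21 to 1.24 pooled and 0.975 to 1.00 stratified. In one of these the false-positive rate was 11% pooled and 6% stratified.
- *Same scenario, centre as a covariate.* Hazard ratio 0.975 with standard error 0.340, the same as stratification in that run.
- *Shares reversed (45% / 75%), mortality 10% / 5%.* Pooled 0.80, stratified 0.98.

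**Cost of stratifying, as the standard error of the log hazard ratio.**

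| Assumed COVID-19 shares | Pooled | Stratified | Increase |
|---|---|---|---|
| 60% in every centre | 0.314 | 0.316 | 0.316/0.314 = 1.006, under 1% |
| 75% / 45% by hospital type | 0.332 | 0.347 | 0.347/0.332 = 1.045, about 5% |
| 80% / 40% by hospital type | 0.334 | 0.358 | 0.358/0.334 = 1.072, about 7% |
| 95, 90, 80, 70, 60, 30 and 10% by centre | 0.334 | 0.406 | 0.406/0.334 = 1.216, about 22% |

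**The case against.** **The text is silent; it does not rule centre out.** This stands. A reader might infer that the authors chose one baseline hazard for all hospitals. The survival sentence lists no adjustment of any kind, so the gap is one of specification.

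**The trajectory sentence covers each outcome measure, so it might include survival.** This does not hold. That sentence goes on to linear and Poisson models for repeated scores, and the Cox model is specified separately.

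**The bias is assumed, not shown.** This stands as a limit. A reader might infer that the plan will overstate harm from COVID-19. The documents give no share or mortality by hospital, and the assumed range crosses 1, so a real difference could equally be hidden.

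**This is one more omitted covariate, and stratification is a preference.** This is partly right. A reader might infer that only stratification can help, but centre as a covariate removes the same confounding when hazards are proportional across centres. Stratification only drops that condition. Centre still deserves its own sentence, because the plan already treats it as a design feature.

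**The comparison is imprecise anyway.** With a standard error of 0.332, the 95% interval spans a factor of exp(1.96 × 0.332) = 1.92 either way. That is true and limits the importance of the point. It does not excuse a bias that can be removed without new data.

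**Conclusion.** The point holds as a gap in specification. Run as written, the survival comparison has no protection against confounding by hospital. With no true effect, the pooled ratio could lie between about 0.68 and 1.54 under the assumed shares and mortality, and it would be about 1.0 if either factor were equal across centres. These figures rest on equal-sized centres, constant hazards and assumed inputs. They show what is possible and do not predict the result.

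A reader might infer that the main result is threatened. It is not: the primary outcome is WHODAS 2.0 disability at 6 months, and the sample size does not rest on survival. This is a worthwhile, inexpensive improvement to one secondary objective.

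**What to change.** Add one sentence to the survival paragraph of Quantitative analysis: the Cox model comparing COVID-19 with other causes will be stratified by treatment centre (seven strata). Centre entered as a covariate is acceptable if hazards are proportional across centres. Robust standard errors alone are not enough, because they leave the point estimate unchanged. Settle this before the analysis, so that the choice is not made with results in view.

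**Cost.** One option in the Stata command and no new data. The loss of precision runs from under 1% to about 20% to 25%, depending on how unevenly COVID-19 patients are spread over centres. A centre with no deaths, or with only one diagnosis group, adds no information to the stratified estimate.

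**Limits.** The change does not replace patient-level adjustment, which the survival paragraph also leaves unstated. It does not require further Kaplan-Meier curves split by hospital type.

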Transferred to a non-participating study centre before ICU discharge assessment	Unable to evaluate
Recent prolonged hospital stay (extended by more than 3 months)	Potential confounding factor
Criteria to stop follow-up	
Re-admission after being ICU discharged	Potential confounding factor
Withdrawal of consent	Incomplete assessment data
Death before 3 or 6 months from ICU discharge	Incomplete assessment data

ICU, intensive care unit; s5q, simple 5 questions scale; CAM-ICU, Confusion Assessment Method for the Intensive Care Unit

Procedure

The planned flow of participants throughout the study is presented in **Figure 1**.

Daily, patients will be screened to identify those who could potentially be discharged from the ICU. Each site coordinator, which is a clinician physiotherapist responsible for the site, will check that the patient is delirium-free (CAM-ICU negative) and cooperative (i.e. using 5 standardised questions: open [close] your eyes; look at me; open your mouth and stick out your tongue; nod your head; raise your eyebrows when I have counted up to five[11]) within 72 hours from ICU discharge. Every patient deemed eligible will be invited to participate and will receive verbal and written information about the study. Patients will be assessed at ICU discharge (T1, defined by the point between medical decision of discharge until 72 hours after), 3 months (T2) and 6 months after ICU discharge (T3). Fifty-eight physiotherapists were trained for the assessments at ICU discharge, which included in-person measurements and self-administered questionnaires. Physiotherapists had to be working in one of the participating ICUs at the time of the training. Training for standardising T1 assessments was delivered by experienced physiotherapists and researchers (ACM, CMO and FGS). For the follow-up assessments (T2 and T3), patients will be contacted via email or telephone to schedule a phone call evaluation performed by trained interviewers.

Baseline data collection

After the patient agreed to participate and signed the informed consent form, the following baseline data will be collected from the patient clinical records: age, gender, body mass index (BMI), highest educational level achieved (no formal

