education, primary school, secondary school, undergraduate or postgraduate), admission diagnosis, Charlson Comorbidity Index, duration of mechanical ventilation, length of hospital stay before ICU admission, ICU length of stay, number of intubations and the maximum level of organ system support received.[12]

Measurement Outcomes

The assessment points and measurement instruments are presented in **Table 2**. Measurement instruments were selected according to the recommended Core Outcome Measurement Set for critical illness survivors.[13,14]

Table 2. Schedule of enrolment and follow-up of the IMPACCT-COVID19 study

	Study period		
	Enrolment		Follow-up
	ICU	3 months from enrolment	6 months from enrolment
Eligibility screening			
Inclusion and exclusion	X		
Invitation to participate			
Informed consent	X		
Patient characteristics			
Age, gender, BMI	X		
Data related to hospitalisation			
Diagnosis, MV days, ICU LOS	X		
Maximum level of organ system support	X		
Pre-admission health and functioning			
Charlson Comorbidity Index	X		
Educational level	X		
Employment status	X	X	X
Clinical Frailty Scale	X	X	X
Physical functioning			
MRC Sum Score	X		
FSS-ICU	X		
Cognitive functioning			
MoCA blind	X	X	X

Mental functioning			
IES-R	X	X	X
HADS	X	X	X
Disability and quality of life			
WHODAS 2.0	X	X	X
EQ-5D-3L		X	X
Sedentary behaviour and physical activity			
Actigraphy			X
GPAQ			X
Survival rate	X	X	X

ICU, intensive care unit; BMI, body mass index; MV, mechanical ventilation; LOS, length of stay; FSS-ICU, Functional Status Score for the Intensive Care Unit; MRC, Medical Research Council; MoCA, Montreal Cognitive Assessment; IES-R, Impact of Event Scale Revised; HADS, Hospital Anxiety and Depression Scale; WHODAS, World Health Organization Disability Assessment Schedule; EQ-5D-3L, European Quality of Life Health Questionnaire 5 domains; GPAQ, Global Physical Activity Questionnaire

When available, we used the Chilean version of each instrument, otherwise, the validated version in Spanish. Trained physiotherapists will take an estimated maximum time of 70 minutes to perform the assessment at ICU discharge (T1). A trained interviewer will take an estimated maximum time of 20 minutes to apply the questionnaires by telephone at 3 (T2) and 6 months (T3) after ICU discharge.

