The primary outcome measure is disability assessed at 6 months after ICU discharge using the World Health Organization Disability Assessment Schedule 2.0 (WHODAS 2.0) which is recommended for critical illness survivors.[8] The WHODAS 2.0 is a self-reported disability questionnaire based on the International Classification of Functioning, Disability, and Health (ICF). It includes 36 questions, organised under six domains (cognition, mobility, self-care, getting along, life activities and participation). Each question must be answered based on the perceived difficulty for performing activities using a 5-point scale (none, mild, moderate, severe and extreme).[15] We will use the Spanish version freely

available at <https://apps.who.int/iris/handle/10665/170500>.[16] The estimated response time ranges from 5 to 10 minutes when evaluated in-person at ICU discharge and 10 to 20 minutes when evaluated by telephone at 3 and 6 months after ICU discharge.

Secondary outcomes measures

Clinical Frailty Scale

The Clinical Frailty Scale (CFS) is a clinical judgment based tool developed for the Canadian Study of Health and Aging to evaluate the degree of frailty in elderly patients.[17] Currently, it is also used for critically ill patients.[18] The CFS evaluates specific domains including physical functioning, activities of daily living (ADL), instrumental ADL, assistance for personal care, comorbidities, and cognition to generate a frailty score using a 9-point scale ranging from 1 (very fit) to 9 (terminally ill). A score greater than 4 is considered fragile.[17] We will use the Spanish version and recommended training material by the developers at the Dalhousie University.[17,19] The estimated scoring time ranges from 1 to 5 minutes evaluated in-person at ICU discharge considering the status 2 weeks before the onset of symptoms.

Medical Research Council Sum Score (MRC-SS)

Limb muscle strength will be assessed using the MRC-SS, which consists in a standardised examination of six muscle groups bilaterally (i.e. shoulder abduction, elbow flexion, wrist extension, hip flexion, knee extension and dorsiflexion).[20] All muscle groups are scored using a 6-point scale between 0 and 5 (0 = no visible /

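### No patient-level adjustment is pre-specified for the non-randomised COVID-19 versus other-cause comparisons, although the main baseline confounders are collected

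*Combined protocol and SAP*

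**What the plan says.** The Introduction of the protocol makes the study comparative. The primary objective contrasts trajectories of impairment between COVID-19 and other-cause survivors. The hypothesis is directional: worse impairment with severe COVID-19 and with higher bed occupancy.

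The Quantitative analysis section answers this with two models. For the repeated outcomes: "The trajectory for each outcome measure will be estimated using longitudinal multilevel regression with robust standard errors", the stated reason being that data come from seven centres. For death, conditional on proportional hazards: "survival will be compared between patients admitted due to COVID-19 vs. other causes using Cox regression". Neither sentence names a patient covariate. The trajectory sentence also names neither COVID-19 status nor time, and the Cox sentence does not mention centre.

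The data needed for adjustment are listed elsewhere. Baseline data collection includes "age, gender, body mass index (BMI), highest educational level achieved", and then "admission diagnosis, Charlson Comorbidity Index, duration of mechanical ventilation". The Clinical Frailty Scale is "evaluated in-person at ICU discharge considering the status 2 weeks before the onset of symptoms", so it describes the patient before the illness. Table 1 gives confounding as the rationale for several exclusion criteria and for stopping follow-up at re-admission.

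**The concern.** Patients are not allocated to COVID-19 or another diagnosis. The two groups may differ in age, schooling, comorbidity and frailty, and each of these plausibly predicts disability, cognition or death whatever the admission diagnosis. A contrast that ignores them mixes case mix with the association the study sets out to measure, and it can hide, exaggerate or reverse it.

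The authors recognise confounding, but they deal with it only by restriction and by stopping follow-up. Excluding people who could not walk independently removes the most disabled. It does not balance age, education, comorbidity or the remaining grades of frailty among those enrolled. Accounting for centre handles clustering, not differences between patients within a centre.

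If covariates are instead chosen once the data are in hand, the result depends on that choice and the reader cannot tell how far.

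**Working it through.** **1. What is collected against what is modelled.** There is no planned figure to reproduce, so the check is a reading of the text.

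| Item | Where collected | Role in any model |
|---|---|---|
| Age, gender, education | Baseline data collection | none stated |
| Charlson index | Baseline data collection; Table 2 | none stated |
| Pre-illness frailty | Clinical Frailty Scale section; Table 2 | none stated |
| Treatment centre | Study design and setting | accounted for in the multilevel models |
| Bed occupancy | not among the listed baseline variables | none stated |

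No section mentions covariates, matching, weighting or a propensity method.

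**2. How large the bias could be.** All confounder figures here are assumptions; the documents give none. For one binary risk factor with risk ratio R, the same in both groups, and prevalence p1 in COVID-19 and p0 in others:

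bias factor = [1 + p1(R − 1)] / [1 + p0(R − 1)]; apparent RR = true RR × bias factor.

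| p1 vs p0 | R | Bias factor | True RR 1.5 appears as |
|---|---|---|---|
| 10% vs 30% | 2 | 1.10/1.30 = 0.85 | 1.27 |
| 10% vs 40% | 3 | 1.20/1.80 = 0.67 | 1.00 |
| 20% vs 20% | any | 1.00 | 1.50 |
| 30% vs 10% (reversed) | 2 | 1.30/1.10 = 1.18 | 1.77 |

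The second and third rows are the extremes over prevalences of 10–20% versus 20–40% and R of 1.5–3. Over that grid the factor runs from 0.67 to 1.00. If the factor is instead commoner in COVID-19 patients, say 40–60% versus 30% with R of 1.5–3, the factor runs from 1.20/1.15 = 1.04 to 2.20/1.60 = 1.38. That would show an association where none exists.

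**3. What adjustment costs in precision.** This illustration borrows two disability scenarios from Table 3, which are framed there as pandemic versus non-pandemic risks, and the 289 patients expected at 6 months. It assumes a two-sided 0.05 test, no clustering, and covariates explaining 10–30% of the exposure variance, so that the effective n is 289 × (1 − R²): 260 at 10% and 202 at 30%. The split between groups is assumed.

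| Scenario | Split | Unadjusted power | Adjusted power |
|---|---|---|---|
| 40% vs 64% | 50:50 | 0.99 | 0.98–0.93 |
| 40% vs 64% | 80:20 | 0.92 | 0.89–0.80 |
| 25% vs 40% | 50:50 | 0.78 | 0.74–0.63 |

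**The case against.** The strongest reply is that silence is not a decision. The section is brief: it omits even the exposure and time terms that the primary objective requires, so missing covariates need not mean that a crude analysis was chosen. That stands. A reader might infer that the authors decided against adjustment; the text does not say so. The accurate statement is that none is pre-specified.

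A second reply is that the size and direction of any bias are unknown. That also stands. The prevalences and risk ratios above are assumed, the walking criterion may make the higher frailty figures unrealistic, and the formula describes a risk ratio at one time point rather than a trajectory. A reader might infer that the COVID-19 association will be understated, or overstated; the documents support neither.

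A third is that the study is observational and only follows how outcomes evolve. This is weaker, because the objectives compare groups and the hypothesis attributes worse outcome to COVID-19 and to occupancy.

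A fourth is that adjustment is not free. Precision falls, and no number of deaths is projected, so the Cox model may carry few covariates. This limits the fix but does not remove the need for it: a precise crude estimate is still confounded.

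**Conclusion.** The point holds in limited form. As written, the analysis plan leads to a COVID-19 versus other-cause contrast with no patient-level adjustment, although suitable pre-exposure variables are already collected. That contrast may be biased. In the assumed illustration a true risk ratio of 1.5 would appear anywhere from 1.00 to 1.50, and above 1.50 if the imbalance is reversed. These figures show what is possible, not what is expected.

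A reader might also infer that the high versus low occupancy comparison is planned as an unadjusted one. The documents do not support this, because the analysis section specifies no occupancy model, variable or cut-off at all. Occupancy matters here because it is the other hypothesised cause of worse outcome and may rise and fall with COVID-19 admissions.

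This should be changed before analysis. It is a cheap improvement and not a reason to doubt the design.

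**What to change.** Add a paragraph to Quantitative analysis:

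- **Trajectory models.** Include COVID-19 status, time and their interaction, adjusted for age, gender, educational level, Charlson index and the pre-illness Clinical Frailty Scale. Name the frailty rating made at ICU discharge, because Table 2 also lists the scale at 3 and 6 months. Report the crude result alongside.
- **Occupancy.** Define bed occupancy at the time of ICU care and put it in the same model as COVID-19 status.
- **Variables to keep out of the main set.** Ventilation days, ICU stay, number of intubations, organ support, MRC-SS and FSS-ICU may be consequences of the illness being compared. Hospital days before ICU admission may be part of the illness course, so use them only in a sensitivity analysis.
- **Cox model.** Pre-specify a reduced set, for example age, Charlson index and frailty, limited by the number of deaths observed.

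The cost is one paragraph of text and no new patient assessments; occupancy needs a definition and a unit-level source, which the protocol does not yet give. The downside is the loss of precision shown above: for 25% versus 40% at an even split, power falls from 0.78 to 0.74–0.63 under the stated assumptions.
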